7.5 POOLING OF CENTERS

No pooling of centers will be done.

7.6 SUBGROUPS

No subgroups summary analysis will be done.

8 DEMOGRAPHIC, OTHER BASELINE CHARACTERISTICS AND MEDICATION

8.1 SUBJECT DISPOSITION AND WITHDRAWALS

The number of subjects screened, number and percentage of subjects who failed screening and reasons for screen failures (Withdrawal of consent, Not meeting eligibility criteria, Decision of investigator, and other) will be tabulated. A listing will also be provided for screen failures with the reason for screen failure.

The number and percentage of subjects in the different analysis sets is also summarized. The listing will be presented for the same together with the reasons for exclusion of subjects from the analysis sets.

Subject disposition will be summarized for all randomized subjects. Subjects who completed the study and discontinued early from the study will be summarized together with the primary reasons (Adverse Events, Death, Withdrawal of Consent, Protocol violation, Lost to follow-up, Investigator does not consider trial participation to be in the subject's best interest, and other) for discontinuation from the study. All percentages will be based on the number of randomized subjects within the treatment group. The same summary table will be presented by initial strata as well as country. Details on end of study/early withdrawals will be provided in a separate by-subject listing.

8.2 DEMOGRAPHIC AND OTHER BASELINE CHARACTERISTICS

All subjects' demographic data and baseline characteristics will be summarized and listed for all subjects in Randomized Set. Summary statistics (n, arithmetic mean, standard deviation, minimum, Q25, median, Q75 and maximum) will be provided for quantitative data (age, baseline weight, height). For qualitative data (gender, ethnicity, race, etc.) frequency tables will be provided. Age will be determined at the time of informed consent. The same summary table will be broken down by the strata as well.

8.2.1 History of Current Hearing Loss and Baseline Hearing Characteristics

History of current hearing loss will be recorded at the TV prior to randomization. The frequencies of the affected ear (left, right, both) as well as the mean, median and range of baseline time from ISSNHL onset (in hours), baseline PTA of the affected ear (in dB), and baseline hearing loss will be tabulated by treatment group. The same summary statistics will be provided by the strata and for the initial hearing loss severity and initial PTA frequency range subgroups.

8.2.2 Baseline Tinnitus Characteristics

The presence or absence of tinnitus (Appendix $\underline{2}$) will be tabulated at the baseline. If tinnitus is present, tinnitus history (onset, tinnitus inducing event, laterality) and tinnitus characteristics (persistence, pitch, sound) will be summarized and listed at the baseline.

For determining TLQ and TAQ at baseline, patients will be asked to fill the 'Tinnitus numerical rating scales Questionnaire (Appendix $\underline{3}$). The tinnitus loudness and annoyance by treatment group will be summarized and listed.

8.2.3 Baseline Word Recognition Score (WRS)

Frequencies for the baseline word recognition score (WRS $_{(80~dB)}$) of the affected ear (\leq 30% and > 30%) as well as the summary statistics for WRS at 60 dB and 80 dB will be tabulated by treatment groups.

8.2.4 Baseline Pregnancy Test Results

Frequencies will be tabulated and listed for the baseline pregnancy test results (positive or negative) by treatment groups.

8.3 MEDICAL HISTORY

Any medical condition already present at the baseline medical assessment will be documented as medical history. The patient's medical history, including a detailed otolaryngological history, will be taken at the TV and documented in the subject's record. Medical history that is clinically relevant will be recorded in the CRF.

Medical history will be coded using the Medical Dictionary for Regulatory Activities (MedDRA). The number and percentage of subjects under each history term, coded by system organ class (SOC) and preferred term (PT), will be summarized and all percentages will be based on the number of subjects in the safety analysis set. If a subject had a medical history term more than once, the subject will be counted only once under any given SOC or PT.

A medical history listing will be provided for all randomized subjects.

8.4 PRIOR MEDICATION AND CONCOMITANT MEDIACTION

Prior medication means all medications taken by a subject before the first dose of IMP administered. Concomitant medication refers to all medication taken by the subject during the trial (encompassing TV until end of follow-up).

Prior and concomitant medication will be classified according to World Health Organization (WHO)-Drug Dictionary prior to providing tabulated overviews. Concomitant medications will be summarized by treatment and presented by WHO Drug

Page 28 of 65

Dictionary Anatomic-Therapeutic-Chemical Code (ATC) level 4 and preferred term in decreasing order in the overall column.

The local anesthetic selected and used by the Investigator in preparation of the intratympanic administration procedure for application of the IMP will not be recorded as concomitant medication, but will be recorded separately with the IMP administration in the CRF.

8.4.1 Other Therapies

As background therapy, an oral corticosteroid course will be offered for 14 days followed by a 5-day taper.

The background corticosteroid treatment may be omitted in case of medical contraindication of oral corticosteroids or if declined by the subject. The other therapies will be listed by subject level.

The following treatments are not allowed during the course of the trial (from TV to FUV4):

- Any concomitant pharmacological or non-pharmacological treatment of ISSNHL-related hearing loss or tinnitus (other than the background therapy that may be started up to 24 hours prior to randomization);
- Any therapy known as potentially ototoxic (e.g. aminoglycosides [systemic or ototopical with middle ear exposure], cisplatin, loop diuretics, quinine etc.);
- Any other pharmacological or non-pharmacological treatment for hearing loss other than the IMP and background therapy unless that treatment was taken for another condition prior to the current ISSNHL incident and started at least 4 weeks prior to randomization; such treatment should be continued unchanged throughout the trial.

9 EFFICACY

All efficacy analyses will be conducted on the Efficacy Analysis Set.

All continuous efficacy data will be summarized descriptively by treatment group and time point including changes from baseline (n, arithmetic mean, standard deviation, minimum, Q25, median, Q75 and maximum). Categorical variables will be summarized with frequencies and percentages by treatment group and time point.

9.1 PRIMARY EFFICACY ENDPOINT AND ANALYSIS

The primary efficacy endpoint is the absolute improvement of PTA in dB from baseline to FUV4 based on the average of the three most affected contiguous audiometric test frequencies. Improvement is defined as the baseline PTA value minus FUV4 value (positive numbers indicating improvement). The descriptive analysis of the primary efficacy endpoint will be performed using Efficacy Analysis Set and Per-protocol Analysis Set.

9.2 SECONDARY EFFICACY ENDPOINT(S) AND ANALYSES

9.2.1 The Main Secondary Efficacy Endpoint Analysis

The main secondary efficacy endpoint is

Absolute improvement in WRS_(80 dB) from baseline to FUV4;

The descriptive analysis of the main secondary efficacy endpoint will be performed using Efficacy Analysis Set and Per-protocol Analysis Set.

9.2.2 The Other Secondary Efficacy Endpoints Analysis

All other secondary efficacy endpoints will be summarized in the Efficacy Analysis Set as described below.

[figure not shown]
- Absolute improvement in PTA from baseline to FUV1, FUV2 and FUV3;
- Absolute improvement in WRS_(80 dB) from baseline to follow-up visits FUV1, FUV2 and FUV3;

The absolute improvements are continuous data which will be summarized descriptively.

• Frequency of complete tinnitus remission in subjects with ISSNHL-related tinnitus at baseline, determined at FUV4. Complete tinnitus remission is achieved when a

Page 30 of 65

subject answers the question about tinnitus presence with "No". Frequency of complete tinnitus remission will be summarized categorically.

Statistical Analysis Plan	Auris Medical Protocol #AM-111-CL-15-0
Version 1.0	

10 SAFETY

All safety analyses will be conducted on the Safety Analysis Set.

10.1 EVALUATION OF SAFETY ENDPOINTS

Primary, secondary and safety endpoints will be analyzed as follows.

10.1.1 Primary Safety Analysis

The percentage of subjects with clinically relevant hearing deterioration (defined as increase in hearing threshold ≥ 10 dB at the average of any two contiguous test frequencies) in the treated ear from baseline to FUV3 will be determined per treatment group and overall for both air conduction or bone conduction results and summarized.

Hearing thresholds will be determined by pure tone audiometry in both ears at 0.25, 0.5, 1, 2, 3, 4, 6, and 8 kHz (air conduction), and at 0.5, 1, 2, 3, 4 kHz (bone conduction). The hearing threshold is defined as the lowest tone level at which the test subject hears the tone, and which is confirmed by a second measure.

Since the audiometry response is a continuous variable, summary statistics will be provided by treatment group at the baseline and FUV3 for the affected ear. The summaries will include actual values and change from baseline for air and bone conduction.

10.1.2 Secondary Safety Analysis

The following secondary safety analyses will be performed:

- 1. The percentage of subjects with clinically relevant hearing deterioration in the treated ear from baseline to FUV1, FUV2 and FUV4 will be summarized in the same way as the primary safety endpoint.
 - A summary table of audiometric assessments for air and bone conduction will be presented with change from baseline to all FUVs. This will cover the primary and the main secondary safety endpoint analysis.
- 2. The difference in occurrence of clinically relevant hearing deterioration from baseline to all FUVs between treated and untreated contralateral ear will be summarized.
- 3. The incidence of post-treatment AEs and SAEs will be described overall and analyzed by relatedness to IMP and to intratympanic IMP administration procedure as shown in section 10.1.2.1.

Page 33 of 65

4. The incidence of AEs will be summarized by system organ class, preferred term, severity and the relationship categories as outlined in section 10.1.2.1. Summaries will be presented by treatment group and overall.

10.1.2.1 Adverse Events

An AE is any untoward medical occurrence in a subject or clinical investigation subject administered a pharmaceutical product and which does not necessarily have to have a causal relationship with this treatment.

An event that emerges during treatment having been absent prior to treatment or worsening relative to the pre-treatment state is defined as treatment emergent adverse event (TEAE).

A SAE is defined as any untoward medical occurrence that

- Results in death
- Is life-threatening
- Requires hospitalization or prolongation of existing hospitalization
- Results in persistent or significant disability or incapacity
- Is a congenital anomaly or birth defect
- Is an important medical event that requires intervention to prevent one of the above

Exceptions are defined in the protocol.

An overall summary table of TEAEs will be provided with the following categories:

- Number and percentage of subjects with TEAEs
- Number and percentage of subjects with a treatment-related TEAE
- Number and percentage of subjects with an intratympanic IMP administration procedure -related TEAE
- Number and percentage of subjects with a TEAE resulting in study withdrawal
- Number and percentage of subjects with a Serious TEAE
- Number and percentage of subjects with a treatment-related serious TEAEs
- Number and percentage of subjects with an intratympanic IMP administration procedure-related serious TEAEs
- Number and percentage of subjects with a TEAE leading to death

The TEAEs will be summarized by SOC and PT by presenting the number and percentage of subjects with a TEAE in each corresponding category

[figure not shown]
The TEAE summary will be produced for the following categories:

[figure not shown]
- TEAEs by SOC and PT
- TEAEs by PT
- Serious TEAEs by SOC and PT
- TEAEs leading to study withdrawal by SOC and PT
- TEAEs by SOC, PT, and maximum severity
- TEAEs by SOC, PT, and strongest relationship to study drug
- Treatment-related TEAEs by SOC and PT
- Administration procedure related TEAEs by SOC and PT
- Treatment-related serious TEAEs by SOC and PT
- Administration procedure related serious TEAEs by SOC and PT
- TEAEs leading to death by SOC and PT

[figure not shown]
In the summary subjects may be counted under multiple SOCs and PTs, but for each SOC and PT, subjects are counted only once. If a subject has the same TEAE on multiple occasions, the highest severity (severe, moderate, mild) recorded for the event will be presented and the highest drug relationship, reclassified into related and not related, will be presented on the respective tables. Missing severity is assumed to be severe, and missing relationships are assumed to have a definite relationship to the IMP or intratympanic IMP administration procedure. Percentages are based on the number of subjects in the safety population.

Listings will be provided for all AEs, AEs leading to discontinuation, and SAEs.

10.2 PHYSICAL EXAMINATION

At TV a general physical examination will be conducted by the Investigator or designee. This examination serves to detect obvious and severe abnormalities, which are to be documented on the respective CRF page. The physical examination should be performed prior to the final determination of the subject's eligibility. Body height and body weight will also be recorded. The results of physical examination along with body height & weight will be listed.

10.3 OTHER SAFETY

All other data, such as concomitant medication or findings from tympanometry, otoscopy, nystagmoscopy or Romberg's test will be presented in individual data listings. Concomitant medication will summarized as specified in the section 8.4.

10.3.1 Pregnancy Test

Women of childbearing potential will have a urine pregnancy test performed with a urine dipstick at the site prior to randomization. This test must be negative for the subject to be randomized and to receive IMP. The pregnancy test will be repeated at FUV4. The results of the pregnancy tests will be listed.

10.3.2 Otology and Audiology Assessments

10.3.2.1 Otoscopy and Microscopy

Otoscopy or microscopy will be performed to ensure that the ear canal of the affected ear is clear and to check for the presence of any relevant otologic disease or abnormality such as otitis media, myringitis, or tympanic membrane perforation. It will be performed with an otoscope or ear microscope and appropriately sized speculum

that best fits the ear canal. Otoscopy or microscopy will be performed at each visit. The results of assessment (normal or abnormal) and different type of abnormality will be summarized by treatment and visit.

10.3.2.2 Tympanometry

Tympanometry will be performed to check the presence of otitis media or Eustachian tube dysfunction. It will be performed at TV and all follow-up visits stating at FUV2 (provided tympanic membrane is closed). The results of assessment (normal or abnormal) will be summarized by treatment and visit.

10.3.2.3 Spontaneous Nystagmus

The number of spontaneous nystagmus beats is measured with Frenzel goggles. The assessment is performed in a darkened room and involves a thorough examination of the eye movements to check if the movements are conjugate. Spontaneous nystagmus beats will be recorded for 30 seconds and documented with the direction of beat. The exam will be performed at each visit (excluding cFUV). Observation of > 10 beats / 30 seconds is considered clinically relevant. The test may also be performed by videonystagmography (VNG). The number of spontaneous nystagmus beats in 30 seconds and results of examination (normal, clinically significant abnormal, and not clinically significant abnormal) will be summarized by treatment and visit.

10.3.2.4 Balance Test

Romberg's test (balance test) will be performed at each trial visit (excluding cFUV). The essential features of the test are as follows:

- 1. The subject stands with feet together, eyes open and hands by the sides.
- 2. The subject closes the eyes while the Investigator, or designee, observes for a full minute.

During the test the Investigator, or designee, stands close by as a precaution in order to stop the subject from falling over and hurting himself or herself.

Romberg's test is positive if the patient sways or falls. The result (negative and positive) of the Romberg' will be summarized by treatment and visit.

10.4 EXTENT OF EXPOSURE

All subjects will receive their single dose IMP administered at the clinical site. Thus the extent of exposure will be one day for all subjects.

10.5 TREATMENT COMPLIANCE

The IMP is administered only once and at the site. Compliance with the background therapy regimen will be checked via the background therapy documentation card. It will be recorded by the Investigator or designee in the CRF and subject records. Background

therapy compliance card will be checked and verified at FUV1 and FUV2, and returned to site at FUV3. All used and/or unused packaging has to be returned by the subject to the site. Treatment compliance will be listed.

Page 39 of 65

11 INTERIM ANALYSES

[figure not shown]
Due to the study being terminated early, the interim analysis is not performed.

Page 40 of 65

Due to the early termination of the study, only 56 subjects are enrolled. The following are changes from the protocol:

- Only partial and missing dates of adverse events and medications are imputed to determine treatment emergence or determine the prior and concomitant medications. All other Imputation of missing values specified in the Protocol section 11.2 is not performed.
- Due to the small sample size, only descriptive analysis is performed in efficacy and safety endpoints.
- Interim analysis will not be performed and conditional power will not be calculated.
- Additional enrollment of subjects based on the results of interim analysis is no longer applicable.
- Tinnitus complete remission is considered given when the subject answers the question about tinnitus presence with "No"; it is not required that in addition both the Tinnitus Loudness Question (TLQ_{Loudest}) and Tinnitus Annoyance Question (TAQ_{Worst}) are rated as zero.
- Addition of analysis of efficacy outcomes by severity subgroup (profound / ≥ 90 dB PTA, severe / < 90 dB PTA at baseline).

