2.2 TIMINGS OF ANALYSES

The primary analysis of safety and efficacy is planned after all enrolled subjects complete the final study visit or terminate early from the study. Only descriptive analyses will be conducted due to the early termination of the study

Page 11 of 65

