3 STUDY OBJECTIVES

3.1 PRIMARY OBJECTIVE

The primary objective of the trial is the confirmation of the efficacy of AM-111 in the recovery of severe to profound idiopathic sudden sensorineural hearing loss (ISSNHL).

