16 PLANNED TABLES, FIGURES AND LISTINGS

Number	Title
Section 14.1.1	Subject Disposition
Table 14.1.1.1	Screen Failures: (All Subjects)
Table 14.1.1.2.1	Number of Subjects Randomized by Country, Site and Treatment Group: (Randomized Set)
Table 14.1.1.2.2	Number of Subjects Randomized by Initial Strata and Treatment Group: (Randomized Set)
Table 14.1.1.2.3	Number of Subjects by Severity of Hearing Loss, Initial Frequency Range, Background Therapy and Treatment Group: Randomized Set
Table 14.1.1.3.1	Subject Disposition: (Randomized Set)
Table 14.1.1.3.2	Subject Disposition by Initial Strata, Country, Severity of Hearing Loss, Initial Frequency Range, Background Therapy and Treatment Group: (Randomized Set)
Section 14.1.2	Protocol Deviations
Table 14.1.2	Protocol Deviations: (Randomized Set)
Section 14.1.3 Section 14.1.3.1	Demographic and Baseline Characteristics Subject Demographic and Baseline Characteristics
Table 14.1.3.1.1	Demographics and Baseline Characteristics: (Randomized Set)
Table 14.1.3.1.2	Demographics and Baseline Characteristics by Initial Strata: (Randomized Set)
Table 14.1.3.1.3	Demographics and Baseline Characteristics by Country: (Randomized Set)
Section 14.1.3.2	Baseline Disease Characteristics
Table 14.1.3.2.1	Baseline Hearing Characteristics: (Randomized Set)
Table 14.1.3.2.2	Baseline Hearing Characteristics by Country: (Randomized Set)
Table 14.1.3.2.3	Baseline Hearing Characteristics by Hearing Loss Severity: (Randomized Set)
Table 14.1.3.2.4	Baseline Hearing Characteristics by Initial Strata: (Randomized Set)
Table 14.1.3.2.5	Baseline Hearing Characteristics by Initial Frequency Range: (Randomized Set)
Section 14.1.3.3	Medical History
Table 14.1.3.3.1	Medical History: (Safety Analysis Set)
Section 14.1.4	Medications (C. C. J. J. J. J. C. J.)
Table 14.1.4.1	Prior Medication: (Safety Analysis Set)
Table 14.1.4.2	Concomitant Medication: (Safety Analysis Set)
Section 14.1.5	Study Drug Exposure
Table 14.1.5	Study Drug Administration: (Safety Analysis Set)
Section 14.2 Section 14.2.1	Efficacy Data Summary Tables Primary Efficacy Parameter
Table 14.2.1.1	Summary of Pure Tone Average (PTA) and Change from Baseline to Follow-up Visits: (Efficacy Analysis Set)

Number	Title
Table 14.2.1.2	Summary of Pure Tone Average (PTA) and Change from Baseline to Follow-up Visits: (Per-Protocol Analysis Set)
Section 14.2.2	Main Secondary Efficacy Parameter

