Table 14.3.4.3.6	Summary of C-SSRS Suicidal Ideation and Behavior: (Safety Analysis Set)
Table 14.3.4.3.7	Summary of C-SSRS Suicidal Ideation Rating: (Safety Analysis Set)
Table 14.3.4.3.8	Summary of C-SSRS Suicidal Ideation Intensity: (Safety Analysis Set)
Table 14.3.4.3.9	Shift of C-SSRS Suicidal Ideation and Behavior: (Safety Analysis Set)
Table 14.3.4.3.10	Shift of C-SSRS Suicidal Ideation Intensity: (Safety Analysis Set)
Table 14.3.4.4.1	Summary of Otoscopy/Microscopy Examinations: (Safety Analysis Set)
Table 14.3.4.4.2	Summary of Tympanometric Assessment: (Safety Analysis Set)
Table 14.3.4.4.3	Shift of Tympanometric Assessment: (Safety Analysis Set)
Table 14.3.4.4.4	Summary of Spontaneous Nystagmus Assessments to Last On-Study Value: (Safety Analysis Set)
Table 14.3.4.4.5	Summary of Balance Test Results: (Safety Analysis Set)

Number	Title
Listing 16.2.1.1	Subject Disposition: (All Subjects)
Listing 16.2.1.2	Eligibility: (All Subjects)
Listing 16.2.2	Protocol Deviations: (Randomized Set)
Listing 16.2.3	Subjects Excluded from Analysis Sets: (Randomized Set)
Listing 16.2.4.1.1	Demographics and Baseline Characteristics: (Randomized Set)
Listing 16.2.4.1.2	Baseline Hearing Characteristics: (Randomized Set)
Listing 16.2.4.2	Medical History: (Randomized Set)
Listing 16.2.4.3	History of Current Hearing Loss: (Randomized Set)
Listing 16.2.4.4	Pregnancy Test: (Randomized Set)
Listing 16.2.5.1	Prior and Concomitant Medication: (Randomized Set)
Listing 16.2.5.2	Study Drug Administration: (Randomized Set)
Listing 16.2.5.3	Background Corticosteroid Therapy: (Randomized Set)
Listing 16.2.6.1	Tinnitus History and Characteristics: (Randomized Set)
Listing 16.2.6.2	Tinnitus Description and Characteristics by Visit: (Randomized Set)
Listing 16.2.6.3	Tinnitus Presence or Absence, and Numerical Rating Scales by Visit:
	(Randomized Set)
Listing 16.2.6.4	Weekly Tinnitus Presence or Absence and Numerical Rating Scales by
	Diary: (Randomized Set)
Listing 16.2.6.5	Patient Global Impression of Change (PGIC): (Randomized Set)
Listing 16.2.6.6	Pure Tone Audiometry (Air): (Randomized Set)
Listing 16.2.6.7	Improvement in Pure Tone Audiometry (Randomized Set)
Listing 16.2.6.8	Pure Tone Audiometry (Bone): (Randomized Set)
Listing 16.2.6.9	Speech Audiometry (WRS at 80 dB in quiet): (Randomized Set)
Listing 16.2.6.10	Speech Audiometry (WRS at 60 dB in quiet): (Randomized Set)
Listing 16.2.6.11	HHIA Questionnaire: (Randomized Set)

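### The SAP's descriptive-only plan drops the protocol's between-arm estimates and intervals along with its tests; small numbers justify dropping the tests but not the estimates

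*SAP*

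**What the plan says.** **Protocol.** Section 11.5.1 plans a repeated-measures mixed ANCOVA. It yields least-squares mean differences at each visit for 0.4 mg/mL minus placebo and 0.8 mg/mL minus placebo, with two-sided 95% and 96 or 99% confidence intervals. Section 11.5.2 uses this model for the primary endpoint, improvement in PTA to FUV4, and adds an FUV4 ANCOVA on imputed data as a sensitivity analysis. Section 11.5.3 plans a logistic regression for complete tinnitus remission, with the treatment effect given as an odds ratio. Section 11 requires changes to planned analyses to be documented in the SAP.

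**SAP.** Section 2.2 says: "Only descriptive analyses will be conducted due to the early termination of the study". The change list (section 12) gives a second reason: "Due to the small sample size, only descriptive analysis is performed in efficacy and safety endpoints". Section 9 says what this means for continuous outcomes: "All continuous efficacy data will be summarized descriptively by treatment group and time point including changes from baseline". The statistics listed are n, mean, SD, minimum, quartiles, median and maximum. For tinnitus, section 9.2.2 says: "Frequency of complete tinnitus remission will be summarized categorically". The efficacy tables in section 16 follow the same pattern; Table 14.2.1.1, for example, is titled "Summary of Pure Tone Average (PTA) and Change from Baseline to Follow-up Visits: (Efficacy Analysis Set". No legible text or table title names a between-arm difference, an odds ratio or an interval.

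**The concern.** The protocol planned two separable things: tests, and estimates with intervals. The SAP removes both, but the reasons it gives bear mainly on the tests. A randomised trial stopped early can still offer an estimated difference with its uncertainty. SAP section 2 says the analyses may go into regulatory submissions and manuscripts, and the retained objectives (efficacy, dose-response) concern differences between arms. With arm means and percentages alone, readers must do their own calculation to see how little a gap between arms, or the absence of one, supports.

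**Working it through.** **1. Protocol and SAP side by side**

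| Item | Protocol | SAP, legible text | Does small size justify dropping it? |
|---|---|---|---|
| Superiority tests and multiplicity procedure | 11.5.2 | Dropped | Yes |
| Interim analysis | 11.9 | Dropped | Yes |
| Dose-minus-placebo differences with intervals (PTA, WRS) | 11.5.1 | Replaced by arm summaries | No |
| Tinnitus odds ratio | 11.5.3 | Replaced by frequencies | No, though the model may need simplifying |

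**2. Inputs.** SAP section 4 gives 56 enrolled. Protocol 5.3.1 counts screening failures as enrolled, so 56 is an upper bound on the number randomised. Allocation is 1:1:1, so an even split is 56/3 = 18.67 per arm. The planned size was 100 per arm. The effect size and SD behind that plan are blacked out in protocol 11.8, so the planned size cannot be reproduced and is not disputed. I assume an SD of PTA improvement of 15 to 30 dB.

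**3. Why dropping the tests is reasonable.** Power is approximately Φ(10/(SD × √(2/n)) − 1.96), with n = 18.67 and a true difference of 10 dB at two-sided 0.05. For SD 15, 20, 25 and 30 dB it is 53%, 33%, 23% and 17%. The 10 dB is the improvement that protocol 10.1.1 calls clinically relevant; it is not stated as a between-arm margin.

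**4. What an interval would show.** The 95% half-width is t(0.975, N − 3) × SD × √(2/n). For N = 56 and SD 15 dB this is 2.006 × 15 × 0.327 = 9.8 dB.

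| Case | SD 15 | SD 20 | SD 25 | SD 30 |
|---|---|---|---|---|
| N = 56, 18.67 per arm | 9.8 | 13.1 | 16.4 | 19.7 |
| N = 42, 14 per arm | 11.5 | 15.3 | 19.1 | 22.9 |
| N = 300, 100 per arm | 4.2 | 5.6 | 7.0 | 8.3 |

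Covariate adjustment is approximated by SD × √(1 − r²) with N − 6 degrees of freedom. With r = 0.5 assumed and N = 56, the range is 8.5 to 17.1 dB.

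**5. Tinnitus, invented counts.** Take remission in 6 of 15 against 4 of 15. The odds ratio is (6/9)/(4/11) = 1.83. The SE of its log is √(1/6 + 1/9 + 1/4 + 1/11) = 0.787, so the 95% interval is 0.39 to 8.57. As a risk difference with a Newcombe score interval, the result is 0.133 (−0.190 to 0.423).

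**6. Can the model be fitted?** For PTA the fixed effects are intercept 1, treatment 2, visit 3, treatment-by-visit 6, baseline 1, frequency range 1 and WRS stratum 1, which is 15 in all. With up to 56 subjects and four visits each, the model is estimable in principle. WRS adds word-list language, which may have several levels.

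**The case against.** **The change is declared.** This stands. The SAP states it with a reason, as protocol section 11 requires. A reader might infer a hidden or undeclared deviation; the documents do not support that.

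**The information is not lost.** This also stands. An unadjusted difference and interval follow by hand from the planned n, mean and SD, and an adjusted one can be refitted from the by-subject listings (16.2.6.7, 16.2.6.9). The planned tables still do not show it.

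**Small numbers do affect adjusted estimation.** This stands in part. The repeated-measures model may fail to converge, the logistic model may separate, and word-list language may not be estimable. That argues for simpler models chosen in advance, not for having no estimate.

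**A 95% interval can be read as a 5% test.** Two doses and two continuous endpoints give four such intervals, unadjusted for multiplicity. The estimation-only wording answers this as far as wording can.

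**The SAP is not fully legible.** Most of pages 31 and 32, in the efficacy section, and parts of 7.1 are not readable. The conclusion rests on the blanket statements in 2.2 and the change list, and on the table titles. These make a planned contrast in the missing text unlikely but cannot exclude it.

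**Severity subgroups.** A reader might infer that the SAP compounds the problem by showing even smaller cells side by side, because the change list includes "Addition of analysis of efficacy outcomes by severity subgroup". The SAP does not support this consistently: section 7.6 says no subgroup summaries will be done, and no efficacy table in section 16 is by severity. That contradiction needs reconciling, but as a separate matter.

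**Conclusion.** The concern holds as a matter of reporting. The protocol planned between-arm estimates with intervals, the legible SAP replaces them with arm summaries, and the stated reasons cover the tests but not the estimates. It would be too strong to call this an error in inference: no p-value, claim or decision rule in the SAP depends on the omission. The likely interval for PTA, about ±10 to ±20 dB for one dose minus placebo, rests on an assumed SD of 15 to 30 dB and an even split of at most 56 subjects with FUV4 data; fewer completers would widen it. These figures illustrate the imprecision that the planned tables leave unstated. The conclusion itself comes from the text and does not depend on them.

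**What to change.** **SAP 9.1 and 9.2.1.** Add: for FUV4 improvement in PTA and in WRS(80 dB), each dose minus placebo is reported with a two-sided 95% confidence interval, for estimation only, with no p-values and no superiority claim. Use the protocol's repeated-measures model, with word-list language added for WRS (protocol 11.5.3). Fix one fallback now, to be used only if that model does not converge: an ANCOVA on observed FUV4 data with treatment, the endpoint's own baseline value and the WRS stratum, plus word-list language for WRS if estimable.

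**SAP 9.2.2.** For tinnitus remission on the SAP's definition, report the protocol's odds ratio with a 95% interval. If the logistic model separates or does not converge, report an unadjusted risk difference with a score interval.

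**SAP section 12.** Declare both fallbacks and the omission of the protocol's 96 or 99% intervals. The ANCOVA fallback must be listed as a change because protocol 11.5.2's version uses imputed data and baseline PTA as covariate.

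**Cost.** Some SAP wording and a few extra tables from data already held. The intervals will be wide, which is the information the reader needs.
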